3.2.2. Neurologists prescribing anti-epileptic drugs

This survey aims to recruit a random sample of 300 neurologists prescribing AEDs and who have been sent the TROBALT Physician's Guide. A sample of 200 neurologists will be recruited from across the following countries (United Kingdom, Sweden, Denmark, Switzerland, Spain, Slovakia and Norway), and up to 100 neurologists will be recruited from Germany. If required, additional EU countries may be included in the survey to reach the minimum recruitment target. The recruitment will be from among those who have prescribed an anti-epileptic drug (AED) at least once in the last 3 months, and who were on the list to which a letter including the Physician's Guide TROBALT was distributed. The survey will aim to recruit at least 75 physicians (from the seven specified countries) and 50 physicians from Germany with experience of prescribing TROBALT for sub-analyses, as these individuals would be expected to be more aware of the risks of TROBALT. The sub-group of neurologists commonly referred to as 'epileptologists' are known from past experience to be the specialists who first initiate prescriptions of a new AED and were therefore specifically targeted for promotional activity by GSK and are the primary target of this survey.

As with the patient population, these numbers reflect a trade-off between what is practical in terms of recruitment, given the relatively low predicted prescribing of TROBALT, and providing sufficient precision around outcome estimates (proportion giving correct responses per question), and also to allow analysis of the sub-sample of neurologists who have prescribed TROBALT.

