3.3.2. Measures to minimise bias in the surveys

The following are measures to minimise bias in the surveys:

- Telephone interviewers are highly trained and use a standardized script to administer interviews.
- All questions will be programmed to ensure that questions are asked in the appropriate sequence. Skip patterns will be clearly indicated. Respondents cannot go back to a question once the question has been answered and cannot skip ahead. All questions must be answered in order to complete the survey.
- Response options presented in a list will be randomized to minimize positional bias.
- Programming will be reviewed by quality control and simulated users (User Acceptance Testing) prior to implementing the survey.

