4.4. Neurologist Outcomes

Neurologist understanding of the significant risks associated with TROBALT will be assessed using a standardised questionnaire.

The primary outcome of this study is the proportion of neurologists that correctly respond to individual survey questions concerning the risks associated with TROBALT. The proportion responding correctly will be tabulated separately for each item in the physician understanding survey instrument. These risks represent those described in the Physician's Guide for TROBALT.

Physician demographic information will be collected at the end of the survey in order to further characterise the respondent population. This will include gender and medical specialty, type of medical practice, years in medical practice. Country in which practice occurs will be collected at the beginning of the survey in order to identify respondents from Switzerland for whom not all questions apply.

At the conclusion of the online survey, the final screen will display a summary of the relevant information from the Physician's Guide.

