Appropriate dose titration may minimise the risk of central nervous system-related adverse events, including hallucination and psychotic disorders.

Date of preparation: May 2011
NECE/RTG/0033/11

Prescribing Information is available on the back page

Trobalt™
retigabine tablets

1. Urinary effects

Urinary retention, dysuria and urinary hesitation were reported in controlled clinical studies with Trobalt, generally within the first 8 weeks of treatment. Trobalt must be used with caution in patients at risk of urinary retention, and it is recommended that patients are advised about the risk of these possible effects.¹

Does your patient have symptoms of urinary retention e.g. hesitancy, poor stream?

Does your patient take drugs that can cause urinary retention e.g. anticholinergics?

Is your patient able to communicate new symptoms of urinary retention?

2. QT interval prolongation

A study of cardiac conduction in healthy subjects has demonstrated that Trobalt titrated to 1200 mg/day produced a QT prolonging effect. A mean increase in Individual Corrected QT Interval (QTcI) of up to 6.7 ms (upper bound of 95% one-sided CI 12.6 ms) was observed within 3 hours of dosing.¹

Caution should be taken when Trobalt is prescribed with medicinal products known to increase QT interval and in patients with known prolonged QT interval, congestive cardiac failure, ventricular hypertrophy, hypokalaemia or hypomagnesaemia and in patients initiating treatment who are 65 years of age and above.¹

In these patients it is recommended that an electrocardiogram (ECG) is recorded before initiation of treatment with Trobalt and in those with a corrected QT interval >440 ms at baseline, an ECG should be recorded on reaching the maintenance dose.¹

Does your patient have a history of cardiac disease?

Does your patient take drugs that are known to cause QT prolongation?

Retigabine has not been shown to cause cardiac arrhythmias in the randomised clinical trials, however patients should be advised to report new symptoms that might indicate a prolonged QT interval, for example palpitations, syncope.

3. Psychiatric effects

During controlled clinical studies, confusional state, psychotic disorders and hallucinations were reported, generally within the first 8 weeks of treatment. It is recommended that patients are

Date of preparation: May 2011
NECE/RTG/0033/11

Trobalt™
retigabine tablets

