19. Using the Treatment Initiation Pack, by which week can the patient reach a dose of 600mg/day?
- 2 weeks
 - **3 weeks**
 - 4 weeks
 - 5 weeks
 - None of the above
20. At what dose has TROBALT been shown to produce a possible QT prolonging effect?
- 600 mg
 - 900 mg
 - **1200mg**
 - 1800 mg
 - I don't know
21. For which patients is it recommended that an ECG is recorded before initiating TROBALT? (Please select all that apply.)
- Patients with hypertension
 - **Patients with congestive heart failure**
 - **Patients with ventricular hypertrophy**

- **Patients with hypokalemia**
 - All of the above
 - None of the above
 - I don't know
22. What should you do in a patient with a QTc of **more** than 440ms before starting TROBALT? (Please select the best response)
- Recheck the ECG 1 week after the first dose
 - Recheck the ECG at monthly intervals
 - **Recheck the ECG after reaching the maintenance dose**
 - I don't know
23. Which new cardiac effects in particular should you warn your patients about after prescribing TROBALT? (Please select all that apply)
- Syncope
 - Palpitations
 - Any other symptoms of arrhythmia
 - **All of above**
 - None of the above
24. How would you classify your primary medical specialty?
- Neurology
 - Neurosurgery
 - Epileptology
 - Other (specify) _____ [FREE TEXT]
 -
25. Have you read the TROBALT information letter that was sent at the launch of TROBALT?
- Yes
 - No
 - I don't know
26. From which of the following sources have you learned about the risks associated with use of TROBALT? (Please select all that apply)
- TROBALT launch letter
 - GlaxoSmithKline medical information
 - Other health care professionals
 - GlaxoSmithKline promotional materials
 - GlaxoSmithKline sales representatives
 - Journal article
 - GlaxoSmithKline-sponsored educational meeting
 - None of the above

27. What is your gender?

- Male
- Female

28. For how many years have you been in medical practice?

- Less than 3 years
- 3-5 years
- 6-10 years
- 11-15 years
- 16-20 years
- More than 20 years
- Prefer not to answer

29. Do you agree to provide your name and address so that we can issue a payment for your time in completing this survey?

- Yes (Record name and address)
- No

Name _____

Address _____

[CLOSING] That ends the survey. Thank you again for your help. The correct answers to the questions about TROBALT follow.

The following are the correct answers to the survey questions about TROBALT.

For which condition is TROBALT approved for use?

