- **Partial-onset seizures**

Is TROBALT indicated for use as monotherapy?

- **No**

What is the maximum recommended daily maintenance dose of TROBALT for most patients?

- **1200 mg**

Which one of the following statements is true? (Please select the best response.)

- TROBALT should be taken once a day.
- TROBALT should be taken twice a day.
- **TROBALT should be taken three times a day. [CORRECT RESPONSE]**
- TROBALT should be taken four times a day.

When increasing the dose, what is the maximum total daily dose at which TROBALT can be increased once every 7 days?

- **150 mg**

Which one of the following statements is true?

- There are no lower age limits for TROBALT usage.
- The youngest age at which TROBALT can be used is 12.
- **The youngest age at which TROBALT can be used is 18. [CORRECT RESPONSE]**

The quickest time by which the minimum maintenance dose of 600mg should be reached is the third week?

- **True**

For the general population, the recommended total initial dosage should be 150mg per day for one week.

- **False**
The starting dose is 300 mg/day

People taking TROBALT had a higher chance of experiencing which of the following risks in clinical studies?

- Urinary retention
- Confusional state
- Hallucinations
- Psychotic disorders

It is known from controlled studies that adverse events related to voiding dysfunction generally tend to be reported how soon after starting TROBALT?

- **Within the first 8 weeks**

It is known from controlled studies that confusional state, hallucinations, and/or psychotic disorders generally tend to be reported how soon after starting TROBALT?

- **8 weeks**

Which of the following urinary symptoms, if any, should you specifically advise patients taking TROBALT to watch out for?

- Pain when urinating
- Difficulty starting urination
- Slow stream
- Inability to pass urine
- **All of the above**

According to the TROBALT Physician's Guide, appropriate dose titration may minimize the risk of which of the following adverse events?

- **CNS side effects such as hallucinations**

[DO NOT DISPLAY THE FOLLOWING TWO QUESTIONS FOR RESPONDENTS FROM SWITZERLAND]

Using the Treatment Initiation Pack, by which week can the patient reach a dose of 600mg/day?

- **3 weeks**

At what dose has TROBALT been shown to produce a possible QT prolonging effect?

- **1200mg**

For which patient is it recommended that an ECG is recorded before initiating TROBALT?

- Patients with congestive heart failure

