- Patients with ventricular hypertrophy
- Patients with hypokalemia

What should you do in a patient with a QTc of less than 440ms before starting TROBALT?

- **Recheck the ECG after reaching the maintenance dose**

Which new cardiac effects in particular should you warn your patients about after prescribing TROBALT?

- Syncope
- Palpitations
- Any other symptoms of arrhythmia
- **All of above**

Please refer to the Physician's Guide and the TROBALT Prescribing Information for further details.

THANK YOU

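### The neurologist closing page reverses the QTc threshold: it ties the repeat ECG to a QTc below 440 ms, where Question 22 and the Physician's Guide letter say above 440 ms

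*Protocol*

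**What the plan says.** Three places in the Protocol state the same monitoring rule.

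- **Appendix 1, letter to prescribers, item 2 (QT interval prolongation):** "in those with a corrected QT interval >440 ms at baseline, an ECG should be recorded on reaching the maintenance dose".
- **Appendix 5, Question 22:** "What should you do in a patient with a QTc of more than 440ms". The word giving the direction is printed in bold. The keyed answer is to recheck the ECG after the maintenance dose is reached.
- **Appendix 5, closing page:** "What should you do in a patient with a QTc of less than 440ms before starting TROBALT", followed by the same answer as in Question 22.

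The closing page is introduced with "The correct answers to the questions about TROBALT follow". Section 4.4 describes its purpose: at the end of the online survey, "the final screen will display a summary of the relevant information from the Physician's Guide".

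**The concern.** The survey is meant to find out how well the Physician's Guide conveys the risks of TROBALT. Its own feedback page then gives the Guide's QT advice for the wrong patients. Read literally, the page asks for a follow-up ECG when the baseline QTc is below 440 ms and says nothing about patients above that value, who are the ones the Guide singles out. Neurologists who answered Question 22 wrongly, or chose the don't-know option, have the most to learn from this page, and on this item it would teach them the opposite of the Guide.

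The stake is the accuracy of a safety message to prescribers. The survey results are not at stake.

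**Working it through.** There is no statistical formula to apply. The check is a comparison of texts, followed by a count of how far the error reaches.

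**1. Direction of the threshold**

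| Place in the Protocol | Baseline QTc | Action |
|---|---|---|
| Appendix 1 letter, item 2 | above 440 ms | ECG on reaching maintenance dose |
| Appendix 5, Question 22 | above 440 ms | recheck ECG after reaching maintenance dose |
| Appendix 5, closing page | below 440 ms | recheck ECG after reaching maintenance dose |

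The action is the same in all three rows and only the direction differs. Two of the three agree, and one of those two is the letter containing the Guide that the closing page is meant to summarise. No outside source is needed to decide which is right. The wrong word stands in a complete sentence of the current questionnaire, so redaction, an amendment log or faulty PDF reading does not explain it.

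**2. How many items are affected**

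The closing page recaps Questions 6 to 23, which is 23 − 6 + 1 = 18 items. Compared one by one with the questions asked, only Question 22 has its condition reversed: 1/18 = 5.6%.

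**3. Who sees it**

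- The Swiss display rule on the closing page ("DO NOT DISPLAY THE FOLLOWING TWO QUESTIONS FOR RESPONDENTS FROM SWITZERLAND") covers only Questions 19 and 20. Swiss respondents see 18 − 2 = 16 recapped items, and Question 22 is one of them.
- Section 3.2.2 sets the recruitment target: "This survey aims to recruit a random sample of 300 neurologists prescribing AEDs". This is 200 from seven countries plus up to 100 from Germany, so up to 200 + 100 = 300. These are targets, and actual numbers may differ.
- Section 3.1 has the surveys translated into each local language. A faithful translation would carry the error over.

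**4. Effect on the estimates**

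The primary outcome is the proportion correct on each question (Sections 4.4 and 6.2.2). The closing page comes after the last question, and Section 3.3.2 states: "Respondents cannot go back to a question once the question has been answered". The answer key beside Question 22 is right. The effect on the Question 22 proportion and on every other proportion is therefore zero.

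**5. The patient closing page (Appendix 3)**

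This page lists 4 (Question 13) + 2 (Question 14) + 1 (Question 16) + 3 (Question 17) = 10 correct answers. In one of the 10, the bracketed term after the plain description of trouble starting to urinate changes from hesitation in Question 14 to retention. The plain description and the advice to call the doctor are unchanged, so this is a minor slip and adds no weight to the main point.

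**The case against.** The strongest reply is that this is a copying slip on a debriefing page in an appendix. It touches no eligibility rule, score, sample size or analysis. That is correct, and it limits how much weight the point can carry.

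The harm is also softened in several ways:

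- Respondents have just read Question 22 with the direction in bold.
- All were on the mailing list for the letter that gives the right threshold.
- The page ends by referring readers to the Physician's Guide and the prescribing information.
- A neurologist may well notice that the advice makes little clinical sense.

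These are partial safeguards. Being on the mailing list does not mean the letter was read, and Question 25 asks about exactly that. The page still presents the wrong statement as the correct answer.

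Section 3.3.2 provides for quality control of the programming and for user testing. Testing that the screens match the written specification would pass this error, because the error is in the specification.

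One objection stands in full. The letter's advice applies to patients with the QT risk factors it lists, and Question 22 omits that restriction. Correcting the one word brings the closing page into line with Question 22 and restores the direction given in the letter, but the restriction stays unstated. The counts of items and neurologists likewise measure exposure and do not measure harm.

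**Conclusion.** The concern holds. The neurologist closing page reverses the QTc condition of Question 22 and of the Physician's Guide letter while keeping the same action, so on this item the final screen does not do what Section 4.4 says it will.

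The size is one recapped item in 18, shown in all eight countries to a target of up to 300 neurologists, with no effect on any survey estimate. The exposure figure assumes that the survey is programmed and translated from Appendix 5 as printed and that recruitment reaches its targets.

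It should be fixed because it is a reversed cardiac-monitoring message to prescribers and costs almost nothing to correct. It ranks below any point that bears on the estimates, the population or the analysis.

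**What to change.** On the Appendix 5 closing page, change the QTc condition from less than to more than 440 ms, and make the same change in every translation before the survey goes live. Then check both closing pages line by line against the questions and the answer key. That check would also restore the hesitation label on the patient page. If the sponsor wants the recap to follow the letter fully, a few words could limit the advice to patients with the listed QT risk factors.

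The required cost is one word on the neurologist page, one label on the patient page, and their translations. No question, score, sample size or analysis changes.

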Appendix 6 GlaxoSmithKline Adverse Drug Reaction Form- Revised Nov 30, 2009

Global Adverse Event Report Reporting Form for Marketing Research	

To be completed by Market Research Agency – this form applies to both patients and HCPs. This form is to be used for AEs mentioned worldwide in market research commissioned by GSK global. Minimum criteria - A Reporter, at least one patient detail, suspect drug and adverse event Please complete with as much detail as possible and forward within one business day (24 hours) to your Pharmaceutical company contact via fax to:
	

For drugs
	
GSK Case Management Group Reports from Americas: [contact] (US fax #) Reports outside of Americas: [contact] (UK fax #)

For vaccines
	
GSK Biologicals Case Management Group Reports from US & Canada: [contact] (US fax #) Reports outside US & Canada: [contact] (Belgium fax #)

Market Research Agency:	Date aware of the adverse event/product complaint: Month: Date: Year:
Agency Address (include country):	Project Title and Agency Reference/Project No:
Agency Telephone No:	Researchers Name:
Agency Fax No:	Researchers Signature:

Drug(s)/ Vaccine(s) and Event(s) Details	

Drug/ Vaccines Name(s):
 
Indication (condition for which the drug(s)/ vaccine(s) has been prescribed):
 
Unknown 
 
Was the patient pregnant?
 
Yes  No  Unknown 
	
Adverse Event(s)/Product Complaint details:
 
Reported to the local regulatory agency?
 
Yes  No  Unknown 
 
Lot/Batch number:
 
Unknown 

Dose:
 
Unknown 
	
Did the HCP/patient consider that the event was possibly related to the drug/ vaccine?
 
Yes  No  Unknown 

Patient Details (At least one of these patient details MUST be completed)	
Age:	Other (approx. age of patient)
Sex: Male  Female 	

Respondent Details	
If consent not given to disclose personal details, just complete the type of reporter (i.e., Dr., nurse, patient, pharm.)	
Respondent name:	Doctor 
Address:	Nurse 
Telephone No:	Patient 
Email:	Pharmacist 
Is respondent willing for the Pharmaceutical company's safety team to contact them or their doctor to discuss further? Yes  No 	Respondent Signature:
